2. RESEARCH PLAN

Purpose of Study:
To compare scar infiltration with 0.5-1% Lidocaine at a dose of 3 mg/kg (max dose 300 mg) or scar deactivation with acupuncture surface release technique to determine which is more effective in reducing pain in adult patients with chronic, post-surgical pain related to the site of incision after low transverse Cesarean section compared to standard of care physical therapy with the McKenzie Method.
Hypotheses, Research Questions, or Objectives:

 • Objective 1: Compare whether a scar infiltration protocol with Lidocaine is more effective than scar deactivation with acupuncture surface release technique at improving pain in adults with chronic, post-surgical pain related to low transverse Cesarean section incision. • Null Hypothesis 1: 0.5-1% Lidocaine at a dose of 3 mg/kg (max dose 300 mg) does not reduce pain outcomes acutely and over time. • Null Hypothesis 2: Scar deactivation with acupuncture surface release technique does not reduce pain outcomes acutely and over time. • Alternative Hypothesis 1: 0.5-1% Lidocaine at a dose of 3 mg/kg (max dose 300 mg) reduces pain outcomes acutely and over time. • Alternative Hypothesis 2: Scar deactivation with acupuncture surface release technique reduces pain outcomes acutely and over time.
Significance:
According to CDC 2015 data, 32% of all births are delivered via Cesarean section ¹ . In patients who undergo Cesarean section, studies estimate 7-18% will experience chronic post-operative pain at the site of their incisional scar ² . These statistics indicate that up to 1 in 6 out of every pregnancy is at risk of developing postoperative pain with an increased risk with each subsequent Cesarean section, and a significant portion of these members will seek care in the primary care clinic.
Military Relevance:
In 2016, the Department of Defense employed 1,288,596 active duty service members, of which 15.9% were women ³ . This age range is consistent with peak childbearing age, which extrapolates to a large portion of the female active duty force with the potential to have children during their military careers. Determining whether Scar infiltration or scar deactivation is more effective treatments for the reduction of chronic, post-surgical low transverse Cesarean section pain in military beneficiaries would result in less: lost duty days, profiles, and physical fitness testing exemptions in our active duty population, as well as an improved quality of life for all DoD beneficiaries. Scar infiltration is a technique using high dose and high volume lidocaine to infiltrate the scar. Scar infiltration uses 40cc to 60cc of 0.5% to 1% lidocaine, which is injected throughout the scar with a goal of 3-4mg/kg per injection. Typically a series of 4 to 5 injections. Scar deactivation is a technique when acupuncture needles are inserted into the skin surrounding the scar and are left in place for approximately 20 minutes and then removed. This can be repeated multiple times.

Background and Review of Literature:

Existing Knowledge: The etiology of chronic, post-surgical abdominal wall and/or pelvic pain after Cesarean section has multiple hypotheses. These possible sources include development of intra-peritoneal adhesions restricting fascial planes, anterior cutaneous nerve entrapment, and disruption of the autonomic nervous system within the intracellular fluid matrix known as an “interference field”^{2,4,5,6,7}. While there is not a clearly established and widely accepted pathophysiological cause to this post-operative pain, studies have estimated that between 7-33% of patients experience chronic peri-incisional pain after Cesarean section with Pfannenstiel incision – a type of abdominal surgical incision that allows access to the abdomen and the most common method for performing Cesarean sections today – defined as pain persisting beyond the period of expected healing, approximately 3 months^{2,7}.

Gaps in Knowledge: Management of chronic peri-incisional pain after Cesarean section requires an extensive workup including laboratory testing (CBC, ESR, Urinalysis, STI testing) and imaging (transvaginal ultrasonography and abdominal CT) to rule out organic causes^{5, 6, 8}. Once a visceral etiology from postoperative pain has been excluded, there is not a well-established guideline dictating standard of care, however treatment can include analgesics such as Acetaminophen or Non-Steroidal Anti-inflammatory Drugs, and in refractory cases suggestive of neuropathic pain Tricyclic Antidepressants, Gabapentin, Pregabalin, and Serotonin-Norepinephrine Reuptake Inhibitors can be used^{5, 6, 8}. If medicinal therapy fails to manage symptoms, consultation for pain management specialists and/or surgical evaluation is often considered^{5, 6, 8}.

Scar deactivation is used as standard of care for treatment and resolution of scar associated pain in patients with a history of Cesarean section by medical acupuncturists, both abdominal and/or low back pain that began after the cesarean section. Scar infiltration with lidocaine has been used in numerous clinical settings, masquerading under different names. Referred to as “Neural Therapy” in Germany, the technique of injecting short-acting local anesthetic into the dermal subcutaneous junction of scar tissue has been widely applied; however there is limited readily available clinical trial evidence supporting its reported effectiveness^{9, 10, 11}. Theoretically, it is postulated that the anti-inflammatory effects of local anesthetics play a role in mitigating the autonomic nervous system disruption of “interference fields” caused by scar tissue^{9, 10, 11}. Local anesthetics promote anti-inflammatory activity through a variety of mechanisms including reversibly inhibiting leukocyte adhesion by interfering with the action of integrins and leukocyte adhesion molecule-1, limiting leukocyte migration, reversible inhibition of phagocytosis, inhibition of phospholipase A2, inhibition of prostaglandins, inhibition of thromboxane release, inhibition of leukotriene release, inhibition of histamine release, reduction in free radical formation, inhibition of cytokine release of IL-1 β , IL-8 and TNF- α ^{12,13}. Additionally, Lidocaine injection is proposed to alleviate nerve entrapment within fascia through hydrodissection, a technique being effectively utilized in the management of carpal tunnel syndrome¹⁴.

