 - Alternating placement of Spring Ten (0.30x40 mm) acupuncture needles to surround scar left in place for a treatment duration of 20 minutes. Needles will be placed at intervals of 1cm to 1.5 cm and will surround the scar with a maximum of 20 needles per treatment.
 - **Group 2: Scar Infiltration with 0.25-1% Lidocaine:**
 - Will consist of calculation of 3 mg/kg dose of 0.5-1% Lidocaine and a dermal followed by subcutaneous injection using 1.5 inch 25 G needle and syringe appropriate for volume based on calculated dose.
 - **Group 3: Physical therapy:**
 - Will be a referral to physical therapy specifying McKenzie protocol treatment for the presenting complaint. The McKenzie protocol is a form of standard of care physical therapy in which the physical therapist tries to find a cause and effect relationship between the positions the patient usually assumes while sitting, standing, or moving, and the location of pain because of those positions or activities. The therapeutic approach requires a patient to move through a series of activities and test movement to gauge the patient's pain response. The approach then uses that information to develop an exercise program designed to centralize or alleviate the pain.

Visit 1 (may be same day as screening visit) (visit window plus or minus 1 week):

Group 1: Scar Deactivation Surface Release Technique protocol (acupuncture):

- Study staff will reconcile medication list (including analgesic medication currently taking).
- Subjects will be weighed (in pounds-not stated weight).
- We will ask what the subjects' expectations are regarding acupunctures effectiveness for chronic, post-surgical pain related to low transverse Cesarean Section.
- The Research Coordinator will record the number of needles placed and the name of the provider performing the acupuncture.
- **Pre-Treatment:**
 - Defense and Veterans Pain Rating Scale (DVPRS)
 - Instruct patients to mark general area of scar on pictures provided on the Patient and Observer Scar Assessment Score (POSAS) Patient Scale.
 - Instruct the PI or AI to complete the POSAS Observer Scale.
- **Post-Treatment:**
 - DVPRS
 - Instruct patients to mark general area of scar on pictures provided the POSAS Patient Scale.
 - Instruct the PI or AI to complete the POSAS Observer Scale.

Group 2: Scar Infiltration with 0.25-1% Lidocaine:

- Study staff will reconcile medication list (including analgesic medication currently taking).

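### The lidocaine volume, concentration, mg/kg and maximum-dose figures do not agree with each other, and the Group 2 procedure omits the 300 mg maximum

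*Combined protocol and SAP*

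**What the plan says.** Three places in the combined protocol and SAP bear on how much lidocaine solution a Group 2 subject receives.

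- **Section 2, Purpose of Study.** The comparison is of "scar infiltration with 0.5-1% Lidocaine at a dose of 3 mg/kg (max dose 300 mg"). The hypotheses that follow repeat the same dose and maximum.
- **Section 2, Military Relevance.** The technique is introduced in general terms: "Scar infiltration is a technique using high dose and high volume lidocaine to infiltrate the scar". The next sentence gives the only volume stated anywhere for it: "Scar infiltration uses 40cc to 60cc of 0.5% to 1% lidocaine, which is injected throughout the scar with a goal of 3-4mg/kg per injection".
- **Section 3, Randomization, Group 2.** The procedure calculates 3 mg/kg of 0.5-1% lidocaine and uses a "syringe appropriate for volume based on calculated dose". It gives no maximum dose and no target volume. The Group 2 heading, here and at Visits 1 to 5, reads 0.25-1%. The procedure text beneath it, and the line on documenting injected volume at Visits 1 to 4, read 0.5-1%.

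Section 2 (Gaps in Knowledge) gives a rationale that is mostly about anti-inflammatory action, then adds one mechanism that depends on fluid: "Lidocaine injection is proposed to alleviate nerve entrapment within fascia through hydrodissection".

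**The concern.** Dose in mg, concentration and volume are tied by one identity, so a protocol can fix two of them freely but not all three. Here a volume range, a concentration range, a mg/kg figure and a mg maximum are all printed, and over much of the stated range they cannot be satisfied together.

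Two things are at stake. The first is consistency on a matter of safety: the descriptive volume, taken at the upper concentration, exceeds the protocol's own maximum, and the section that staff would work from does not restate that maximum. The second is what the lidocaine arm is. The protocol calls the technique high-volume and names hydrodissection as a possible mechanism, yet the text supplied leaves the volume for a given mg dose open. Section 6 names treatment group and time as the fixed effects, with no term for concentration or volume, so any such variation would be absorbed into the arm.

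**Working it through.** **Inputs.** Volume 40-60 cc, concentration 0.5-1% and goal 3-4 mg/kg (Section 2, Military Relevance). Dose 3 mg/kg, maximum 300 mg, 0.5-1% (Section 2, Purpose of Study). Heading concentration 0.25-1% (Section 3, Group 2). The documents give no weight distribution, so the body weights in the table are illustrative.

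**Formulas.** A c% solution holds 10 × c mg/mL. Dose = the smaller of 3 mg/kg × weight and 300 mg. Volume = dose ÷ (10 × c).

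**Where the plan's own volume reproduces.** At 0.5% (5 mg/mL):
- 40 mL × 5 = 200 mg, and 200 ÷ 3 = 66.7 kg
- 60 mL × 5 = 300 mg, and 300 ÷ 3 = 100 kg

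So 40-60 cc is what 3 mg/kg delivers at 0.5% for subjects of 66.7 to 100 kg. From 100 kg upward the maximum holds the volume at 60 mL.

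**Where it does not.**
- At 1% (10 mg/mL), 40 mL holds 400 mg and 60 mL holds 600 mg. Against the maximum these are 400 ÷ 300 = 1.33 and 600 ÷ 300 = 2.0 times. The maximum allows 300 ÷ 10 = 30 mL, so no body weight reaches 40 mL.
- The highest concentration at which 40 mL fits within 300 mg is 300 ÷ 40 = 7.5 mg/mL, or 0.75%. At 3 mg/kg that needs 100 kg or more.
- At 0.5% and below 66.7 kg, 40 mL is not reached. A 60 kg subject gets 180 ÷ 5 = 36 mL.
- The 4 mg/kg end of the descriptive range does not rescue 1%. Reaching 40 mL would take 400 ÷ 4 = 100 kg, but the 400 mg still exceeds 300 mg.

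**Volume permitted for the same mg dose (3 mg/kg, 300 mg maximum applied).**

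| Weight | Dose | 1% | 0.5% | 0.25% (heading only) |
|---|---|---|---|---|
| 50 kg | 150 mg | 15 mL | 30 mL | 60 mL |
| 60 kg | 180 mg | 18 mL | 36 mL | 72 mL |
| 70 kg | 210 mg | 21 mL | 42 mL | 84 mL |
| 100 kg | 300 mg | 30 mL | 60 mL | 120 mL |

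The ratio is 1 ÷ 0.5 = 2 over the range in the text, and 1 ÷ 0.25 = 4 if the heading is taken literally.

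**Effect of omitting the maximum from Section 3.** At 3 mg/kg the 300 mg maximum starts to bind at 100 kg. A calculation from the Section 3 text alone gives 3 × 120 = 360 mg at 120 kg, against 300 mg under the Purpose of Study.

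**The case against.** The strongest reply is that the 40-60 cc figure is background. It sits in a paragraph on military relevance, describes common practice (including a typical number of injections), and is never repeated in Section 3. The arm procedure already settles the order of calculation: dose first, volume as a consequence. The ranges also overlap in part, since at 0.5% they fit the study dose from 66.7 kg upward. This stands. The volume is not an operating target, and there is no basis for saying that staff would dose from it.

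A reader might go further and infer that the lidocaine arm in fact contains two different treatments, that a difference between sites would be a volume difference, or that a null result would mean the described technique was never given. The documents do not support this. They permit a two-fold spread but do not show that one occurs, and nothing describes different practice at the two sites. The Procedure Instructions, listed as an attachment in Section 12, were not available and may fix the concentration. Volume is also not established as the active component: hydrodissection is one added proposal after a longer pharmacological rationale. Weight and total volume are both collected at each treatment visit, so concentration could be back-calculated if the 3 mg/kg rule was followed.

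The reply does not remove the conflict. The descriptive text uses the study's own concentration range and carries the only volume given. Setting it aside leaves two discrepancies in the operative section: the missing maximum, and the heading that disagrees with the text under it.

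**Conclusion.** The figures contradict each other and need to be reconciled. At 1% the described volume is 1.33 to 2.0 times the stated maximum and cannot be met at any weight. At 0.5% it is met only from 66.7 kg. Within Section 3, the 300 mg maximum is absent and the concentration is given as both 0.25-1% and 0.5-1%. The text supplied therefore allows the same mg dose in volumes that differ two-fold, or four-fold on the heading's figures.

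The arithmetic rests only on the protocol's numbers. The spread in volume rests on one assumption: that no document outside those supplied fixes the concentration. It is a possibility left open by the wording, not an observed feature of the arm. The sample size and power figures are not affected.

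**What to change.** The sponsor should reconcile Section 2 (Purpose of Study and Military Relevance) with the Group 2 text and headings in Section 3 (Randomization and Visits 1 to 5). Concentration range, mg/kg figure, maximum dose and volume should agree wherever they appear, and the arm procedure should carry the same limits as the stated purpose. The Procedure Instructions should be checked against the reconciled text. Which values to keep is the sponsor's clinical decision, and none is suggested here.

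The cost is a few lines of protocol wording and a consistency check of one attachment. No change to design, sample size or analysis follows from it.

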3. RESEARCH DESIGN AND METHODS

Research Design and Methods:

Active duty members and DoD beneficiaries, age 18 years of age or older, meeting the inclusion/exclusion criteria will be offered an opportunity to participate. They will be recruited from the clinics located at Nellis AFB and Scott AFB. All of the below items are research-related unless marked as 'standard of care':

Pre-Eligibility review: Subjects who responded to advertisements or recruitment letters or have given their permission to be contacted will be approached by a study staff member to discuss the subject's interest in the research study and to receive a pre-eligibility screening for study participation. The attached "Pre-Eligibility Review Script" will be used and response will be recorded. If the subject is interested in participating in the study, the study staff member will schedule a screening visit while the subject waits on the phone or in-person, in order to confirm the schedule appointment with the subject. Following the pre-screening procedure, the script will be shredded.

Screening Visit:

- Obtain and document signed Informed Consent document and HIPAA Authorization.
- Review past medical history to verify the inclusion/exclusion criteria including previous encounter, medication list (including analgesic medication currently taking), co-morbidities, demographics, and problems list.

- Record date of birth, age, gender, race, ethnicity, DoD ID, current email address, height (inches), weight (in pounds-not stated weight), obstetrical history, history of relevant pain and interventions.
- Instruct subjects to discontinue any current acupuncture treatment at the onset of entering the study. It is theorized that any acupuncture treatment can have a positive or a negative effect on treatment response regardless of the technique or treatment indication.
- If the subject is an active duty member, we will ask:
 - Have you or are you currently on a fitness restriction for this condition.
 - If so, what are/were the dates of the restriction?

Randomization:

- Subjects will be randomized into one of three research-related treatment groups using block randomization with repeated measures:
 - **Group 1: Scar Deactivation Surface Release Technique protocol:**
 - Alternating placement of Spring Ten (0.30x40 mm) acupuncture needles to surround scar left in place for a treatment duration of 20 minutes. Needles will be placed at intervals of 1cm to 1.5 cm and will surround the scar with a maximum of 20 needles per treatment.
 - **Group 2: Scar Infiltration with 0.25-1% Lidocaine:**
 - Will consist of calculation of 3 mg/kg dose of 0.5-1% Lidocaine and a dermal followed by subcutaneous injection using 1.5 inch 25 G needle and syringe appropriate for volume based on calculated dose.
 - **Group 3: Physical therapy:**
 - Will be a referral to physical therapy specifying McKenzie protocol treatment for the presenting complaint. The McKenzie protocol is a form of standard of care physical therapy in which the physical therapist tries to find a cause and effect relationship between the positions the patient usually assumes while sitting, standing, or moving, and the location of pain because of those positions or activities. The therapeutic approach requires a patient to move through a series of activities and test movement to gauge the patient's pain response. The approach then uses that information to develop an exercise program designed to centralize or alleviate the pain.

Visit 1 (may be same day as screening visit) (visit window plus or minus 1 week):

Group 1: Scar Deactivation Surface Release Technique protocol (acupuncture):

- Study staff will reconcile medication list (including analgesic medication currently taking).
- Subjects will be weighed (in pounds-not stated weight).
- We will ask what the subjects' expectations are regarding acupunctures effectiveness for chronic, post-surgical pain related to low transverse Cesarean Section.
- The Research Coordinator will record the number of needles placed and the name of the provider performing the acupuncture.
- **Pre-Treatment:**
 - Defense and Veterans Pain Rating Scale (DVPRS)
 - Instruct patients to mark general area of scar on pictures provided on the Patient and Observer Scar Assessment Score (POSAS) Patient Scale.
 - Instruct the PI or AI to complete the POSAS Observer Scale.
- **Post-Treatment:**
 - DVPRS
 - Instruct patients to mark general area of scar on pictures provided the POSAS Patient Scale.
 - Instruct the PI or AI to complete the POSAS Observer Scale.

Group 2: Scar Infiltration with 0.25-1% Lidocaine:

- Study staff will reconcile medication list (including analgesic medication currently taking).
- Subjects will be weighed (in pounds-not stated weight).
- We will ask what the subjects' expectations are regarding lidocaine's effectiveness for chronic, post-surgical pain related to low transverse Cesarean Section.
- The Research Coordinator will document the total volume of 0.5-1% Lidocaine injection.
- **Pre-Treatment:**
 - DVPRS

- Instruct patients to mark general area of scar on pictures provided on the POSAS Patient Scale.
- Instruct the PI or AI to complete the POSAS Observer Scale.
- Post-Treatment:
 - DVPRS
 - Instruct patients to mark general area of scar on pictures provided the POSAS Patient Scale.
 - Instruct the PI or AI to complete the POSAS Observer Scale.

Group 3: Physical Therapy:

- Study staff will reconcile medication list (including analgesic medication currently taking).
- Subjects will be weighed (in pounds-not stated weight).
- We will ask what the subjects' expectations are regarding physical therapy's effectiveness for chronic, post-surgical pain related to low transverse Cesarean Section.
- Subjects will be given a study diary and asked to track the dates and duration of their physical therapy treatments.
- DVPRS
- Instruct patients to mark general area of scar on pictures provided on the POSAS Patient Scale.
- Instruct the PI or AI to complete the POSAS Observer Scale.

Visit 2 (4 weeks after visit 1 (visit window plus or minus 1 week)):

Group 1: Scar Deactivation Surface Release Technique protocol (acupuncture):

- Study staff will reconcile medication list (including analgesic medication currently taking).
- Subjects will be weighed (in pounds-not stated weight).
- The Research Coordinator will record the number of needles placed and the name of the provider performing the acupuncture.
- Pre-Treatment:
 - DVPRS
 - Instruct patients to mark general area of scar on pictures provided on the POSAS Patient Scale.
 - Instruct the PI or AI to complete the POSAS Observer Scale.
- Post-Treatment:
 - DVPRS
 - Instruct patients to mark general area of scar on pictures provided the POSAS Patient Scale.
 - Instruct the PI or AI to complete the POSAS Observer Scale.

Group 2: Scar Infiltration with 0.25-1% Lidocaine:

- Study staff will reconcile medication list (including analgesic medication currently taking).
- Subjects will be weighed (in pounds-not stated weight).
- The Research Coordinator will document the total volume of 0.5-1% Lidocaine injection.
- Pre-Treatment:
 - DVPRS
 - Instruct patients to mark general area of scar on pictures provided on the POSAS Patient Scale.
 - Instruct the PI or AI to complete the POSAS Observer Scale.
- Post-Treatment:
 - DVPRS
 - Instruct patients to mark general area of scar on pictures provided the POSAS Patient Scale.
 - Instruct the PI or AI to complete the POSAS Observer Scale.

Group 3: Physical Therapy:

- Study staff will reconcile medication list (including analgesic medication currently taking).
- Subjects will be weighed (in pounds-not stated weight).
- We will record the information from the study diary and remind them to track the dates and duration of their physical therapy treatments.
- DVPRS
- Instruct patients to mark general area of scar on pictures provided on the POSAS Patient Scale.

- Instruct the PI or AI to complete the POSAS Observer Scale.

Visit 3 (8 weeks after visit 1) (visit window plus or minus 1 week):

Group 1: Scar Deactivation Surface Release Technique protocol (acupuncture):

- Study staff will reconcile medication list (including analgesic medication currently taking).
- Subjects will be weighed (in pounds-not stated weight).
- The Research Coordinator will record the number of needles placed and the name of the provider performing the acupuncture.
- ***Pre-Treatment:***
 - DVPRS
 - Instruct patients to mark general area of scar on pictures provided on the POSAS Patient Scale.
 - Instruct the PI or AI to complete the POSAS Observer Scale.
- ***Post-Treatment:***
 - DVPRS
 - Instruct patients to mark general area of scar on pictures provided the POSAS Patient Scale.
 - Instruct the PI or AI to complete the POSAS Observer Scale.

Group 2: Scar Infiltration with 0.25-1% Lidocaine:

- Study staff will reconcile medication list (including analgesic medication currently taking).
- Subjects will be weighed (in pounds-not stated weight).
- The Research Coordinator will document the total volume of 0.5-1% Lidocaine injection.
- ***Pre-Treatment:***
 - DVPRS
 - Instruct patients to mark general area of scar on pictures provided on the POSAS Patient Scale.
 - Instruct the PI or AI to complete the POSAS Observer Scale.
- ***Post-Treatment:***
 - DVPRS
 - Instruct patients to mark general area of scar on pictures provided the POSAS Patient Scale.
 - Instruct the PI or AI to complete the POSAS Observer Scale.

Group 3: Physical Therapy:

- Study staff will reconcile medication list (including analgesic medication currently taking).
- Subjects will be weighed (in pounds-not stated weight).
- We will record the information from the study diary and remind them to track the dates and duration of their physical therapy treatments.
- DVPRS
- Instruct patients to mark general area of scar on pictures provided on the POSAS Patient Scale.
- Instruct the PI or AI to complete the POSAS Observer Scale.

Visit 4 (16 weeks after visit 1) (visit window plus or minus 1 week):

Group 1: Scar Deactivation Surface Release Technique protocol (acupuncture):

- Study staff will reconcile medication list (including analgesic medication currently taking).
- Subjects will be weighed (in pounds-not stated weight).
- The Research Coordinator will record the number of needles placed and the name of the provider performing the acupuncture.
- ***Pre-Treatment:***
 - DVPRS
 - Instruct patients to mark general area of scar on pictures provided on the POSAS Patient Scale.
 - Instruct the PI or AI to complete the POSAS Observer Scale.
- ***Post-Treatment:***
 - DVPRS
 - Instruct patients to mark general area of scar on pictures provided the POSAS Patient Scale.

- Instruct the PI or AI to complete the POSAS Observer Scale.

Group 2: Scar Infiltration with 0.25-1% Lidocaine:

- Study staff will reconcile medication list (including analgesic medication currently taking).
- Subjects will be weighed (in pounds-not stated weight).
- The Research Coordinator will document the total volume of 0.5-1% Lidocaine injection.
- Pre-Treatment:
 - DVPRS
 - Instruct patients to mark general area of scar on pictures provided on the POSAS Patient Scale.
 - Instruct the PI or AI to complete the POSAS Observer Scale.
- Post-Treatment:
 - DVPRS
 - Instruct patients to mark general area of scar on pictures provided the POSAS Patient Scale.
 - Instruct the PI or AI to complete the POSAS Observer Scale.

Group 3: Physical Therapy:

- Study staff will reconcile medication list (including analgesic medication currently taking).
- Subjects will be weighed (in pounds-not stated weight).
- We will record the information from the study diary and remind them to track the dates and duration of their physical therapy treatments.
- DVPRS
- Instruct patients to mark general area of scar on pictures provided on the POSAS Patient Scale.
- Instruct the PI or AI to complete the POSAS Observer Scale.

Visit 5 (20 weeks after visit 1) (visit window plus or minus 1 week):

Group 1: Scar Deactivation Surface Release Technique protocol (acupuncture):

- Study staff will reconcile medication list (including analgesic medication currently taking).
- Subjects will be weighed (in pounds-not stated weight).
- DVPRS
- Instruct patients to mark general area of scar on pictures provided on the POSAS Patient Scale.
- Instruct the PI or AI to complete the POSAS Observer Scale.
- We will record the subjects self-reported reduction in pain severity since the beginning of the study (reported a percentile (i.e. 10%, 20%, etc.).
- We will ask if the subjects' expectations were met regarding acupunctures effectiveness for chronic, post-surgical pain related to low transverse Cesarean Section.

Group 2: Scar Infiltration with 0.25-1% Lidocaine:

[figure not shown]
- Study staff will reconcile medication list (including analgesic medication currently taking).
- Subjects will be weighed (in pounds-not stated weight).
- DVPRS
- Instruct patients to mark general area of scar on pictures provided on the POSAS Patient Scale.
- Instruct the PI or AI to complete the POSAS Observer Scale.
- We will record the subjects self-reported reduction in pain severity since the beginning of the study (reported a percentile (i.e. 10%, 20%, etc.).
- We will ask if the subjects' expectations were met regarding lidocaine's effectiveness for chronic, post-surgical pain related to low transverse Cesarean Section.

Group 3: Physical Therapy:

- Study staff will reconcile medication list (including analgesic medication currently taking).
- Subjects will be weighed (in pounds-not stated weight).
- DVPRS
- Instruct patients to mark general area of scar on pictures provided on the POSAS Patient Scale.

- Instruct the PI or AI to complete the POSAS Observer Scale.
- We will record the subjects self-reported reduction in pain severity since the beginning of the study (reported a percentile (i.e. 10%, 20%, etc.).
- We will ask if the subjects' expectations were met regarding physical therapies effectiveness for chronic, post-surgical pain related to low transverse Cesarean Section.

This study will follow all FDA requirements for the safe use of the acupuncture needles. The Food and Drug Administration (FDA) regulates acupuncture needles (see 21 CFR 880.5580) as a class II medical device, because they are intended for use in the cure, mitigation, treatment, or prevention of disease in man or are intended to affect the structure or function of the body of man. The needles being used are Spring Ten 0.30x40mm Acupuncture needles (see figure 1 below), which are exempt from premarket notification by the FDA for use in acupuncture and will be used in accordance with their FDA approved labeling.

a. Interventions and Observations:

Patient and Observer Scar Assessment Score (POSAS): Scar evaluation tool which has been shown to be appropriate for evaluation of linear scars, such as the Pfannenstiel incision, with good reliability and internal consistency. This scale evaluates for pain and itching at the scar site, change in color of the skin, change in stiffness or thickness of the scar, change in irregularity of the scar and overall assessment of change in the scar.

Secondary Outcomes:

- Reduction in the POSAS score
- Reduction in related symptoms including
 - dyspareunia,
 - decreased libido, or
 - Seemingly unrelated symptoms.

b. Setting:

Female (DoD beneficiaries) age 18 years or older meeting the inclusion criteria will be offered an opportunity to participate at Scott AFB, Scott AFB O'Fallon Family Medicine Residency Clinic located at [name] and Nellis AFB.

c. Date(s):

March 2019-May 2022

d. Subjects:

Female DoD beneficiaries meeting the inclusion criteria will be offered an opportunity to participate at Scott AFB and Nellis AFB. No other special populations (e.g., children, military basic trainees, prisoners, detainees) will be recruited.

e. Inclusion/Exclusion Criteria:

Inclusion Criteria	
 Female DoD beneficiaries age 18 years or older 3 months or greater postpartum with abdominal and/or back pain starting after low transverse Cesarean section scar. If subject has had prior Scar Deactivation with Surface Release Technique for cesarean section scar they must have completed a washout period of 12 weeks or more.
Exclusion Criteria	
 Pregnant Prior Scar Deactivation with Surface Release Technique for cesarean section scar within the last 12 weeks. Ever had Prior Scar Infiltration with Lidocaine for cesarean section. Active cellulitis surrounding scar

	
 Revision of Cesarean section scar Vertical incision or emergent Cesarean section
--	---

f. Source of Research Material:						
Will you be using private information in this study?		 Yes				
If Yes,  protected health information (PHI) held by a covered entity						
Use of identifiers with private information						
Identifiers to be Used?	Column A Looked at by research team	Column B Recorded on enrollment log, subject list, or key list	Column C Recorded on data collection tool (survey, spreadsheet, etc.)	Column D Recorded on specimen containers	Column E Shared w/ others not on research team	Column F Stored after study ended
NONE						
Names						
Study codes linked to individuals' identities using a key only accessible by the researcher						
Phone/Fax Numbers						
E-mails						
DoD ID#						
Coding Plan?						
Describe the method that will be used to create and assign unique study codes to data.	The unique study code will be assigned in sequential order beginning with 001 at each recruiting site. Subjects at Nellis AFB will be named such as NE001 and subjects at Scott AFB will begin with SC001. The code will be placed in a Master Key of identifiable PHI/PII for each subject at each collaborating site					
Describe the method that will be used to create and assign unique study codes to specimens.	 N/A, not collecting specimens					
What is the format of the key?	 Electronic					
Who will have access to the key?	Principal Investigator and/or Designated Research Coordinator at each study site					
Where will the key be stored and how will it be protected?	
Location(s): Each collaborating site will maintain a Master Key of identifiable PHI/PII that will be kept in an electronic database separate from the coded, de-identified research data, which will be encrypted, password protected and the access will be restricted to the PI and/or Designated Research Coordinator. The Master Key will not be stored on any non-government or personal computers or laptops. At the conclusion of the study, the data from each site will be de-identified prior to review and analysis.
 
Confidentiality measures: The coded research data will be kept in a locked cabinet in a locked office and only the research department has the key. The coded research data will be retained until the conclusion of the research study. Once a Final Report has been approved by the IRB, all the paper records will be de-identified and any key linking the subject to their records will be destroyed, based on AFI 33-332, "The Air Force Privacy and Civil Liberties Program" and the National Institute of Standards and Technology Special Publication (NIST SP 800-88) for the approved methods to destroy PII. The anonymized research data will not be utilized for further research activity beyond the protocol stipulations without additional IRB approval.
					

Complete the table.

Source of Research Material per Participant (Procedures)	# Routine Care	# Research Driven	# Total Procedures
DVPRS	0	9	9
POSAS	0	9	9
Acupuncture	0	4	4
Lidocaine	0	4	4

McKenzie Protocol	0	4	4
g. Instrumentation: N/A			

